2.3 Timing of interim analyses and design adaptations

This study has also been categorized as voluntary European Post Authorization Safety Study (PASS). Therefore, regular interim analyses will be performed during the course of the study. Interim analyses will be performed as need by the Sponsor and approximately at the following time points:

- Q4 2017
- Q4 2019
- Q4 2021
- Q4 2023

2.4 Definition of end of the study

End of study is defined as either 10 years from FPFV (or until 10-Jun-2023 in the UK) or when all patients on this study have permanently discontinued pasireotide treatment or have been able to obtain commercial supply according to local regulations or have been able to receive the drug through country-specific programmes outside of this clinical trial (applicable to Brazil, France, Germany, India, Italy, Malaysia, Mexico, Peru and Thailand) and the end of treatment visit and all safety follow-up procedures have been performed for each patient, whichever comes first.

2.5 Early study termination

The study can be terminated at any time for any reason by Recordati. Should this be necessary, the patient should be informed as soon as possible and should stop taking study labeled drug. Assessments should be performed as described in Protocol Section 7.1.3 for a prematurely withdrawn patient. The investigator may be informed of additional procedures to be followed in order to ensure that adequate consideration is given to the protection of the patient's interests. The investigator will be responsible for informing IRBs and/or ECs of the early termination of the trial.

2.6 STATISTICAL SOFTWARE

SAS version 9.4 or higher will be used in all analyses.

3 CHANGES IN THE PLANNED ANALYSIS OF THE STUDY

Not applicable.

4 STATISTICAL METHODS

This section contains information that will be used to draft CSR Section 9.7 on statistical analysis.

4.1 Data analysis general information

The statistical analysis of these data will be performed by IQVIA personnel in accordance with the data analysis section, Section 10, of the study protocol which is available in [Appendix 16.1.1 of the CSR]. Important information is given in the following sections and details are provided, as applicable, in [Appendix 16.1.9 of the CSR].

Data included in the analysis

Final analyses will be performed when all patients have been followed for 3 months (84 days) following the last dose of pasireotide LAR treatment and for 1 month (30 days) following the last dose of pasireotide s.c. treatment.

All events with start date before or on the cut-off date and end date after the cut-off date will be reported as 'continuing at the cut-off date'. The same rule will be applied to events starting before or on the cut-off date and not having documented end date. This approach applies, in particular, to adverse event reports. For these events, the end date will not be imputed and therefore will not appear in the listings.

It is planned that the data from all centers that participate in this trial will be pooled and analyzed. Unless otherwise specified, qualitative data will be described using frequency and percentages, while quantitative data, will be described using descriptive statistics: n, mean, standard deviation, median, minimum, and maximum.

All data will be summarized and listed by indication (acromegaly, Cushing's disease and Others) and formulation (s.c. and LAR).

For the formulation, the variable can be derived from the DAR panel from the DARTYP1C variable, the values captured are 533 and 838 which correspond to Pasireotide LAR and Pasireotide s.c., respectively.

The indication will be derived based upon the parent study number from the HIS panel using the PRVSTY2C variable as described in the following Table 2-1 with the exception of parent study numbers CSOM230C2110E and CSOM230B2219. For those two parent studies, the indication will be derived from the parent study data sets as shown in Table 2-2.

Parent study number	eCRF	Indication	Indication group
CSOM230B2201E	78	Acromegaly	Acromegaly
CSOM230B2208E	79	Cushing's disease	Cushing's disease
CSOM230D2203	81	NET other pituitary and EAS	Other diseases
CSOM230B2305	82	Cushing's disease	Cushing's disease
CSOM230X2203	83	Dumping syndrome	Other diseases
CSOM230C2305	84	Acromegaly	Acromegaly
CSOM230G2304	85	Cushing's disease	Cushing's disease
CSOM230C1202	86	Acromegaly or pituitary	Acromegaly
CSOM230C2402	87	Acromegaly	Acromegaly
CSOM230X2404	115	Melanoma	Other diseases
CSOM230X2404	116	Melanoma	Other diseases
CSOM230C2413	117	Acromegaly	Acromegaly
CSOM230B2411	125	Cushing's disease	Cushing's disease
CSOM230XDE04	126	Prostate cancer	Other diseases
CSOM230D2401	136	Pituitary adenomas	Other diseases
CSOM230DIC03	137	NET	Other diseases

Table 2-1 Derivation of the indication information – Part 1

Table 2-2Derivation of the indication information – Part 2

Parent study number	eCRF code	Parent data set	Parent data set variable	Indication	Indication group
CSOM230C2110E1 CSOM230C2110E1 CSOM230B2219	80 80 114 or 113	ADMG ADMG AIDENT	CLIND CLIND DISTYP3A	Carcinoid Acromegaly Acromegaly	Other diseases Acromegaly Acromegaly
CSOM230B2219	114 or 113	AIDENT	DISTYP3A	Cushing's disease	Cushing's disease

Treatment period

The overall observation period will be divided into two mutually exclusive segments:

on-treatment period: from day of first dose of study medication in the roll-over study to 3 months (84 days) following the last dose of pasireotide LAR treatment and to 1 month (30 days) following the last dose of pasireotide s.c. treatment.

post-treatment period: starting at 3 months+1 day (day 85) following the last dose of pasireotide LAR treatment and at 1 month+1 day (day 31) following the last dose of pasireotide s.c. treatment.

Safety summaries (tables, figures) include only data from the on-treatment period. In addition, a separate summary for death including on treatment and post treatment deaths will be provided. In particular, summary tables for adverse events (AEs) will summarize only on-treatment events, with a start date during the on-treatment period (treatment-emergent AEs).

However, all safety data (including those from the post-treatment period) will be listed and those collected during the post-treatment period will be flagged.

Study Treatment

Study drug and investigational treatment refer to pasireotide. Patients are to use the study treatment based on the parent protocol.

Date of first/last administration of study drug

The start date of study drug is defined as the first date when a non-zero dose of study drug was administered in the roll-over study and recorded on the Dosage Administration Record (DAR) eCRF.

The date of last administration of study drug is defined as the last date when a non-zero dose of study drug was administered and recorded on DAR eCRF.

Laboratory data

Pregnancy tests will be listed overall and by indication and formulation.

4.2 *Patient disposition, demographics and other baseline characteristics*

4.2.1 Patient disposition

Patient disposition will be summarized overall and by indication and formulation using the Safety Set. The number (%) of treated patients included in the Safety Set will be presented. The number (%) of patients in the Safety Set who are still on treatment, who discontinued the study treatment and the reason for discontinuation will be presented overall

The following summaries will be provided (with % based on the total number of Safety Set patients):

- Number (%) of patients who are still on-treatment at the time of data cut-off or final data base lock;
- Number (%) of patients who discontinued the study treatment;
- Number (%) of patients with primary reason for end of study treatment (based on patient status entered in the 'Study phase completion' page);

- Number (%) of patients who have entered the post-treatment follow-up safety evaluation (based on the 'Study completion' page);
- Number (%) of patients who have discontinued from the post-treatment follow-up (based on the 'Study Completion' page);
- Number (%) of patients with primary reason for end of study (based on patient status entered in the 'Study completion' page);

Listings will be provided overall and by indication and formulation for disposition, informed consent, inclusion/exclusion criteria using the Safety set.

4.2.2 Patient demographics and other baseline characteristics

Demographic information will be summarized and listed overall and by indication and formulation using the Safety Set. Demographic summary will include age and gender.

Categorical data (e.g. gender, age groups: 18 to <65 years, and \geq 65 years) will be summarized by frequency counts and percentages. Continuous data (e.g. age) will be summarized by descriptive statistics (N, mean, median, standard deviation, minimum and maximum, 25th and 75th percentiles).

Demographic listing will include country, center, current patient ID, age and gender.

Medical history and ongoing medical conditions, including disease-related conditions and symptoms entered on (e) CRF will be summarized and listed overall and by indication and formulation. Separate summaries will be presented for ongoing and historical medical conditions. The summaries will be presented by primary system organ class (SOC) and preferred term (PT). Medical history and current medical conditions will be coded using the Medical Dictionary for Regulatory Activities (MedDRA) terminology. The MedDRA version used for reporting will be specified in the CSR and as a footnote in the applicable tables/listings.

A listing of parent study history (parent study number, parent patient ID, parent study indication and parent study formulation) will also be provided using the Safety Set.

4.3 Treatments (study treatment, rescue medication, concomitant therapies, compliance)

4.3.1 Study treatment / compliance

Dose administration data will be summarized overall and by indication and formulation using the Safety Set.

5 VARIABLES AND ENDPOINTS

Objectives and related endpoints are described in Table 5-1 below altogether with the planned analysis of collected data.

Table 5-1 Objectives	and related endpoints	
Objective	Endpoint	Analysis
Primary		
To evaluate long term safety data, i.e. SAEs and AEs	Frequency and severity of AEs/SAEs	The assessment of safety will be based on the frequency and severity of adverse events (AEs) and serious adverse events (SAEs)
Secondary		
To evaluate clinical benefit as assessed by the investigator	Proportion of patients with clinical benefit as assessed by the investigator at scheduled visits	Proportion of patients with clinical benefit as assessed by the investigator will be summarized at scheduled visits
Other secondary		
Not applicable	Not applicable	Not applicable

5.1 HANDLING OF MISSING DATA AND OUTLIERS

5.1.1 Study drug

Below mentioned imputation rules will be used in case of missing or partial end date of study drug.

Scenario 1

If the last date of study drug is after the cut-off date or is completely missing and there is no end of treatment eCRF page and no death date the patient should be considered to be on-going and use the cutoff date for the analysis as the last dosing date

Scenario 2

If the last date of study drug is completely or partially missing and there is EITHER an end of treatment eCRF page OR a death date available then imputed last dose date:

- = 31DECYYYY, if only Year is available and Year < Year of min (EOT visit date, death date)
- = Last day of the month, if both Year and Month are available and Year = Year of min (EOT visit date, death date) and Month < the month of min (EOT visit date, death date)
- = min (EOT visit date, death date), for all other cases

The imputed date will be compared with start date of study drug.

If the imputed date < start date of study drug, then last date of study drug is set to start date of study drug; otherwise, use the imputed date.

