7.4.1 Adverse events (AEs)

Treatment emergent AEs are defined as those that started on or after the study medication, or those that started before study medication but worsened afterwards. AEs starting after 84 days following the last dose of pasireotide LAR treatment and after 30 days following the last dose of pasireotide s.c. treatment are not considered treatment emergent AEs. Summary tables for adverse events (AEs) have to include only AEs that started or worsened during the on-treatment period, the **treatment-emergent** AEs. However, all safety data

(including those from the post-treatment periods) will be listed and those collected during the post-treatment period are to be flagged.

The incidence of treatment-emergent adverse events (new or worsening from baseline) will be summarized by system organ class and/or preferred term, severity based on CTCAE grades (version 4.03), type of adverse event, relation to study treatment. The summary will include AEs regardless of study-drug relationship. The same analysis will be repeated for SAEs.

All treatment emergent AEs and SAEs will be listed. In this listing, the information on the relationship to study treatment will be included.

Adverse events will be coded using the Medical dictionary for regulatory activities (MedDRA) terminology using the latest available MedDRA version at the time of the analyses and the information of MedDRA version will be specified in the footnote of relevant outputs.

The following selection of AEs will be listed and summarized separately using Safety Set. AEs will be summarized for all grades and for grade 3 or 4 side-by-side.

- AEs
- SAEs
- AEs leading to study drug discontinuation
- AEs requiring dose adjustment or interruption
- AEs requiring additional therapy
- Adverse events of special interest (AESI)

For the legal requirements of ClinicalTrials.gov and EudraCT, two required tables on treatment- emergent adverse events which are not serious adverse events with an incidence greater than 5% and on treatment-emergent serious adverse events and SAE suspected to be related to study treatment will be provided by system organ class and preferred term on the safety set population.

If for a same patient, several consecutive AEs (irrespective of study treatment causality, seriousness and severity) occurred with the same SOC and PT:

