7.4.2 Deaths

Separate summaries for on-treatment death and all deaths (including on-treatment and post- treatment) will be produced by primary system organ class and preferred term overall and by indication and formulation using the Safety Set. On-treatment and all

deaths will be listed overall and by indication and formulation and post treatment deaths will be flagged.

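### SAP 5.1.1, Scenario 2: a last-dose date with a known month in an earlier calendar year is overwritten by the EOT or death date

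*SAP*

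**What the plan says.** SAP 5.1.1, Scenario 2, applies when the last date of study drug is wholly or partly missing and there is an EOT page or a death date. Write R for the earlier of the EOT visit date and the death date. There are three rules:

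1. Year only: "31DECYYYY, if only Year is available and Year < Year of min (EOT visit date, death date").
2. Year and month: "Last day of the month, if both Year and Month are available and Year = Year of min (EOT visit date, death date"), with the further condition that the month is earlier than the month of R.
3. Everything else: "min (EOT visit date, death date), for all other cases".

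The imputed date is then compared with the study drug start date and moved up to it if it falls earlier. That is the only later check. SAP section 3 lists no changes to the planned analysis.

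The last-dose date is used in these places:

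- SAP 4.1 ends the on-treatment period by reference to it. For LAR the period runs "to 3 months (84 days) following the last dose of pasireotide LAR treatment". For the s.c. formulation it runs "to 1 month (30 days) following the last dose of pasireotide s.c. treatment".
- SAP 7.4.1 uses the same limits for treatment-emergent AEs; for s.c., events starting "after 30 days following the last dose of pasireotide s.c. treatment are not considered treatment emergent AEs".
- SAP 7.4.2 plans "Separate summaries for on-treatment death and all deaths", so the split between on-treatment and post-treatment deaths depends on it.
- SAP 7.3 uses it for duration of exposure and, through that, dose intensity.

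**The concern.** The second rule tests year and month separately, and the year test is an equality. A record with both year and month known, in a year before R, fails rule 1 because the month is available and fails rule 2 because the years differ. Rule 3 then assigns R.

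That result lies outside the recorded month and the recorded year. It is also later than the date given to a record that holds less information. The neighbouring rules show a different intention: a year-only record stays within its year, and a month in the same year as R stays within its month. SAP 4.1 says: "The date of last administration of study drug is defined as the last date when a non-zero dose of study drug was administered". The partial record places that dose in a particular month, and the imputed date contradicts it.

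A last-dose date set too late lengthens the on-treatment window. AEs and deaths that belong to the post-treatment period can then enter the treatment-emergent and on-treatment tables, which carry the primary objective. Exposure is overstated unless death or the data cut-off caps it. For LAR, where cumulative dose is the sum of recorded injections, dose intensity is understated. For s.c. the effect on dose intensity cannot be stated, because the SAP does not say how cumulative dose is built up.

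**Working it through.** The SAP gives no worked example for this rule, so there is no figure of its own to reproduce. The rules come from SAP 5.1.1, the windows from SAP 4.1 and 7.4.1, and the exposure formulas from SAP 7.3. All calendar dates below, and the 13 LAR injections of 40 mg, are illustrative assumptions.

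**Imputed dates.** The corrected rule gives the last day of the recorded month whenever the recorded year-month is before the year-month of R.

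| Recorded | R | SAP as written | Corrected | Difference |
|---|---|---|---|---|
| 2019 only | 20JAN2020 | 31DEC2019 (rule 1) | 31DEC2019 | 0 days |
| DEC2019 | 20JAN2020 | 20JAN2020 (rule 3) | 31DEC2019 | 20 days |
| NOV2019 | 20JAN2020 | 20JAN2020 (rule 3) | 30NOV2019 | 51 days |
| OCT2019 | 20JAN2020 | 20JAN2020 (rule 3) | 31OCT2019 | 81 days |
| NOV2019 | 20DEC2019 | 30NOV2019 (rule 2) | 30NOV2019 | 0 days |

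The last row shows that an earlier month in the same year is handled correctly.

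**On-treatment window, NOV2019 with R = 20JAN2020.**

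- s.c.: 20JAN2020 + 30 = 19FEB2020, against 30NOV2019 + 30 = 30DEC2019.
- LAR: 20JAN2020 + 84 = 13APR2020, against 30NOV2019 + 84 = 22FEB2020.

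**Deaths.** Take an s.c. patient with NOV2019 who died on 20JAN2020 and has no earlier EOT date. As written, the last dose is 20JAN2020 and the death is on-treatment. Even a dose on the last day of November closes the window on 30DEC2019, 21 days before the death. A LAR patient with the same dates is not misclassified: a dose as early as 01NOV2019 keeps the window open to 24JAN2020.

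**Exposure, first dose 19DEC2018, last dose NOV2019, R = 20JAN2020.**

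- s.c. (last date − first date + 1): 398 days as written, 347 corrected.
- LAR (last date + 27 − first date + 1): 425 days as written, 374 corrected. Dividing by 30.4375 gives 13.963 and 12.287 months. Cumulative dose is 13 × 40 = 520 mg. Dose intensity is 520/13.963 = 37.2 against 520/12.287 = 42.3 mg/month; 374/425 = 0.880, a fall of 12.0%.
- LAR with exposure capped by death on 20JAN2020: 398 days as written against 374. Dose intensity is 39.8 against 42.3 mg/month; 374/398 = 0.940, a fall of 6.0%.

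The percentage shrinks with longer treatment. The excess stays at 51 days, so the uncapped ratio is D/(D + 51), where D is the corrected duration. A first dose on 29SEP2017 gives 820/871, a fall of 5.9%. A first dose on 10JUN2013, when the study opened, gives 2392/2443, a fall of 2.1%.

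**Share of partial dates affected.** Assume only the day is missing, the last dose is equally likely on any day of a 365-day year, and R falls g days later. The year boundary is crossed when the last dose is in the final g days of the year, so the share is g/365.

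| g | Share misdated | Days past the recorded month |
|---|---|---|
| 7 | 7/365 = 1.9% | 1 to 7 |
| 28 | 28/365 = 7.7% | 1 to 28 |
| 84 | 84/365 = 23.0% | 54 to 84 |

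Among only those records where R falls in a later month, which are the ones rule 2 should catch, the shares are 7/84 = 8.3%, 28/336 = 8.3% and 84/365 = 23.0%.

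**The case against.** The strongest case is that the rule will seldom be used and does little damage when it is.

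- Protocol 9.4 has missing values queried. Protocol 7.1.5 asks for a prompt EOT visit and has the EOT form give the date of stopping treatment, so a partial dosing date can usually be resolved where that form exists.
- LAR injections are given at the site, so a missing day is least likely for the formulation that gives the largest percentages.
- The 12.0% fall in dose intensity rests on about one year of treatment; longer exposure gives much less.
- The death example needs several conditions together: s.c. treatment, an unresolved date, no EOT visit for weeks, a year boundary and then death.
- The 84-day gap draws on the quarterly s.c. visit schedule, which governs resupply and not discontinuation.
- Protocol 8.2.2 limits SAE reporting after the follow-up period to suspected related events, so fewer late events exist to be misplaced.
- A longer window counts more events as treatment-emergent, usually the cautious direction for AE incidence. All safety data are still listed, all deaths are summarised, and no hypothesis is tested.
- The SAP 4.1 definition refers to a date recorded on the dosing form, and imputation begins where that complete date is absent.

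Most of this stands as a limit on reach, and it is why the point is minor. On the last item, what stands is that the imputed date contradicts the month that was recorded. None of it repairs the rule: imputation exists for dates that queries leave unresolved, and in this case the rule gives a date the record itself rules out. The cautious direction for AE counts does not extend to exposure.

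**Conclusion.** The rule is wrong as written. Any last-dose date with a known year and month in a calendar year before R is set to R, and no other part of the SAP or protocol overrides this. In the worked case the date is 20 to 81 days past the end of the recorded month, and the on-treatment window is extended by the same amount. One s.c. death pattern is tabulated as on-treatment although the window had closed at least 21 days earlier.

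The overall effect cannot be sized, because the documents give no count of partial last-dose dates; it is probably small. The shares of 1.9% to 23.0% apply only to day-missing records and rest on evenly spread last doses and a fixed gap to EOT or death. A prompt EOT visit points to the low end. The severity is minor.

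**What to change.** Reword the second rule of Scenario 2 so that year and month are compared jointly: impute the last day of the recorded month whenever year and month are both known and that year-month is earlier than the year-month of min(EOT visit date, death date). The other two rules can stay. Year-only, same-year and same-month records keep the dates they get now.

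The cost is one line of SAP text and the matching line of code, with no new data. SAP section 2 has decisions on the final analysis made before database lock, so the change belongs before then.

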5.1.2 AE date imputation

Date imputation is the creation of a new, complete date from a partial one according to an agreed and acceptable algorithm. Missing date for AE will be handled according to rules

specified below. A partial date is simply an incomplete date e.g. DDOCT2001: the days are missing from this DDMMMYYYY date.

Partial AE start dates, if left partial, would ultimately mean the following:

It would not be possible to place the AE in time. Therefore the treatment/dosage at the time of the event would be unknown. So the event could not be reported/summarized appropriately – if at all.

Therefore it is important to perform date imputation to ensure that as many data events are represented as correctly as possible. Of course partial and/or missing dates should also be caught as edit checks and passed back to the investigator for resolution.

There **will be no** attempt to impute the following:

- **Missing** AE start dates
- AE start dates **missing the year**
- Partial/missing AE end dates

Table 5-1AE/Treatment date abbreviations

	Day	Month	Year
Partial AE start date	<not used=""></not>	AEM	AEY
Treatment start date (TRTSTD)	<not used=""></not>	TRTM	TRTY

The following matrix Table 5-3 describes the possible combinations and their associated imputations. In the light grey boxes the upper-text indicates the imputation and the lower text the relationship of the AE start date to the treatment start date (TRTSTD).

Table 5-2AE partial date imputation algorithm

	AEM Missing	AEM < TRTM	AEM = TRTM	AEM > TRTM
AEY Missing	NC	NC	NC	NC
AEY < TRTY	Before TRTSTD	Before TRTSTD	Before TRTSTD	Before TRTSTD
	(D)	(C)	(C)	(C)
AEY = TRTY	Uncertain	Before TRTSTD	Uncertain	After TRTSTD
	(B)	(C)	(B)	(A)
AEY > TRTY	After TRTSTD	After TRTSTD	After TRTSTD	After TRTSTD
	(E)	(A)	(A)	(A)

Table 5-3AE/treatment date relationship and imputation legend

Relationship	
Before TRTSTD	Indicates AE start date prior to Treatment Start Date
After TRTSTD	Indicates AE start date after Treatment Start Date
Uncertain	Insufficient to determine the relationship of AE start date
	to Treatment Start Date

Imputation Calculation

convention/imputation
MONYYYY
ISTD+1
MONYYYY
ULYYYY
ANYYYY

The following Table 5-5 gives a few examples.

Table 5-4	AE imputation e	xample scenario	S	
Partial AE start	Treatment start	Relationship	Imputation	Imputed date
date	date		calculation	
12mmyyyy	200CT2001	Uncertain	NC	<blank></blank>
ddmmm2000	200CT2001	Before	(D)	01JUL2000
ddmmm2002	200CT2001	After	(E)	01JAN2002
ddmmm2001	200CT2001	Uncertain	(B)	210CT2001
ddSEP2001	200CT2001	Before	(C)	15SEP2001
ddOCT2001	200CT2001	Uncertain	(B)	210CT2001
ddNOV2001	200CT2001	After	(A)	01NOV2001

Any AEs with partial/missing dates will be displayed as such in the data listings.

Any AEs which are continuing as per data cut-off will be shown as 'ongoing' rather than the end date provided.

Incomplete date for death

All dates must be completed with day, month and year.

If the day or month is missing, death will be imputed to the maximum of the last contact date (excluding the date of death) and the following:

- Missing day: 15th of the month and year of death
- Missing day and month: July 1st of the year of death

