7.1.2 Screening

There will be no screening period for this study. At the enrollment visit, the patient will need to complete a written informed consent. Once consented, patients will be evaluated for eligibility via the inclusion and exclusion criteria.

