8.1 Adverse events

8.1.1 Definitions and reporting

An adverse event is defined as the appearance of (or worsening of any pre-existing) undesirable sign(s), symptom(s), or medical condition(s) that occur after patient's signed informed consent has been obtained.

Abnormal laboratory values or test results occurring after informed consent constitute adverse events only if they induce clinical signs or symptoms, are considered clinically significant, require therapy (e.g., hematologic abnormality that requires transfusion or hematological stem cell support), or require changes in study medication(s).

Any ongoing adverse events from the parent study will be captured as medical history in the roll-over database. Any AE that begins (or worsens) after signing of the informed consent for the roll-over and during the 30-day (or 28-day) or 84-day (12 week) safety follow up period defined in the parent protocol should be reported in both clinical databases.

Adverse event monitoring should be continued for at least 30 days for patients receiving the s.c. formulation and 84 days for those receiving the LAR formulation (or 5 half-lives), whichever is longer) following the last dose of study treatment. Adverse events (including lab abnormalities that constitute AEs) should be described using a diagnosis whenever possible, rather than individual underlying signs and symptoms. When a clear diagnosis cannot be identified, each sign or symptom should be reported as a separate Adverse Event.

Adverse events will be assessed according to the current version of Common Terminology Criteria for Adverse Events (CTCAE).

If CTCAE grading does not exist for an adverse event, the severity of mild, moderate, severe, and life-threatening, corresponding to Grades 1 - 4, will be used. CTCAE Grade 5 (death) will not be used in this study; rather, information about deaths will be collected through the EOT eCRF page.

The occurrence of adverse events should be sought by non-directive questioning of the patient (subject) during the screening process after signing informed consent and at each visit during the study. Adverse events also may be detected when they are volunteered by the patient (subject) during the screening process or between visits, or through physical examination, laboratory test, or other assessments. As far as possible, each adverse event should be evaluated to determine:

1. The severity grade (CTCAE Grade 1-4)
2. Its duration (start and end dates)

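### AEs still without a start date or start year after queries have no treatment-emergent default, so SAP 4.1 and 5.1.2 read together leave them out of the AE tables

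*SAP*

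**What the plan says.** SAP 5.1.2 explains why incomplete AE start dates are imputed. If a date is left partial, the event cannot be placed in time and the dose at onset is unknown: "So the event could not be reported/summarized appropriately". It then lists what stays untouched. Under "There will be no attempt to impute the following" come wholly missing start dates, "AE start dates missing the year", and partial or missing end dates. In the imputation matrix the row for a missing start year is coded NC in all four columns. The worked example that has only a day ends with a blank date and a relationship labelled uncertain. The same section sends incomplete dates back to the investigator through edit checks and keeps these AEs in the listings.

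SAP 4.1 sets the filter for the tables: "summary tables for adverse events (AEs) will summarize only on-treatment events, with a start date during the on-treatment period". SAP 7.4.1 says "Treatment emergent AEs are defined as those that started on or after the study medication", adds events that began earlier and worsened, and closes the window at 84 days (LAR) or 30 days (s.c.) after the last dose. It does not mention an unknown start.

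The protocol limits what can enter the AE database. Section 8.1.1: "Any ongoing adverse events from the parent study will be captured as medical history in the roll-over database". It also defines an AE as arising or worsening after consent. Section 7.1.2: "There will be no screening period for this study". Section 2.2 has treatment begin once the patient is consented and eligible. After the 30/84-day follow-up, section 8.2.2 asks only for SAEs the investigator suspects are related.

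**The concern.** The primary endpoint is the frequency and severity of AEs and SAEs. A record with no usable start date cannot pass a filter that requires one, so it contributes to no treatment-emergent count. That covers the AE, SAE and AESI tables and the treatment-emergent tables for the public registries. Such an omission can only lower the counts. For a rare SAE term, one lost record could turn a count of 1 into 0.

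The default also sits oddly in this design. In a roll-over study where earlier AEs go to medical history and dosing follows consent, an AE of unknown date is more likely to have started on treatment than off it. If a programmer instead chose to count such records, the primary tables would rest on a choice the SAP does not state.

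**Working it through.** **1. Reproduce the SAP's examples.** The inputs are the matrix and examples in SAP 5.1.2, with treatment start 20OCT2001. The code legend is partly cut off in the extracted text, so the codes were read together with the examples: A = first of the month, B = treatment start + 1 day, C = 15th of the month, D = 1 July, E = 1 January.

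| Known part of AE start | Code | Imputed date | On or after first dose? |
|---|---|---|---|
| day only (12) | NC | blank | cannot be tested |
| 2000 | D | 01JUL2000 | no |
| 2002 | E | 01JAN2002 | yes |
| 2001 | B | 21OCT2001 | yes |
| SEP2001 | C | 15SEP2001 | no |
| OCT2001 | B | 21OCT2001 | yes |
| NOV2001 | A | 01NOV2001 | yes |

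All 7 examples agree with the matrix.

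**2. Count the cells.** The matrix has 4 × 4 = 16 cells: A 4, B 2, C 4, D 1, E 1, NC 4. The four NC cells are the whole missing-year row. They give no date and no relation to first dose. The two uncertain cells with a known year (code B) are placed one day after first dose and therefore counted.

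**3. Apply the table filter.** SAP 4.1 requires a start date inside the on-treatment period, and a blank date cannot meet that. The worsening clause in SAP 7.4.1 does not rescue the record, because protocol 8.1.1 makes a worsening a second entry that needs its own start date.

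**4. Compare the collection window with the on-treatment window.** Collection runs from roll-over consent. The on-treatment period runs from first roll-over dose to last dose + 84 days (LAR) or + 30 days (s.c.). The differences are the interval from consent to first dose, which is short by design, and late SAEs suspected to be related. Most undated records are therefore likely to be treatment-emergent. This is an inference from the rules, not a figure in the documents.

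**5. Illustrate the size.** The documents give no rate of undated AEs. Let *f* be the share of AE records still undated after queries and *q* the share of records that are truly treatment-emergent, taken as equal for dated and undated records. Both are assumptions.

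- Excluding undated records counts (1 − f)q, a relative undercount of f.
- Counting all of them gives (1 − f)q + f, a relative overcount of f(1 − q)/q.

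| f | Undercount if excluded | Overcount if counted, q = 0.90 | Overcount if counted, q = 0.99 |
|---|---|---|---|
| 0.1% | 0.1% | 0.011% | 0.001% |
| 1% | 1% | 0.111% | 0.010% |
| 5% | 5% | 0.556% | 0.051% |

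For f = 1% and q = 0.90: 0.01 × 0.10 / 0.90 = 0.111%. Counting gives the smaller error whenever (1 − q)/q < 1, that is, whenever q is above one half. These are shares of records. If incidence is counted per patient, losing one record often changes nothing.

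**The case against.** The case against is strong on size and on wording.

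- **Exclusion is not written as a rule.** A reader might infer that the SAP orders undated AEs out of the tables. It does not. The result comes from joining 5.1.2 to the filter in 4.1, and 7.4.1 is silent. This stands, but the silence is itself the gap: following both stated rules drops the record, and nothing tells a programmer to do otherwise.
- **The sentence about events that could not be summarised** might be read as the SAP's verdict on undated records. It is the SAP's reason for imputing partial dates. It shows that the SAP sees the problem, not what happens to the records left blank.
- **Upstream controls should leave few such records.** SAP 5.1.2 and protocol 9.4 require queries. Protocol 8.1.1 asks for start and end dates as far as possible, and AEs are sought at monthly or 12-weekly visits. SAEs are due within 24 hours of awareness, with full verification of SAE documentation (8.2.2, 9.2). This stands and is why the effect is probably small. It does not supply a rule for what remains, and listings are not counts.
- **Code B is not a like-for-like precedent.** A known year bounds the date, whereas a missing year in a study open for about 10 years does not. This stands. The comparison shows only the direction in which the SAP resolves doubt elsewhere.
- **A blanket default leaves the formulation column open.** Results are reported by formulation, and protocol Appendix 9 describes s.c. rescue use in patients on LAR. This stands, so the fix has to cover it.

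**Conclusion.** The point holds as a gap in the SAP. An AE or SAE whose start date or start year is still missing after queries has no stated treatment-emergent status, and the stated rules taken together keep it out of the primary-endpoint tables. Any resulting error runs one way, towards fewer events. It rests on two assumptions: that some records stay undated at database lock, and that more than half of those are treatment-emergent. The collection rules make the second likely.

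Three stronger readings are not supported. The documents do not show that every undated AE must follow the first dose: AEs count from consent, and late suspected-related SAEs are reportable. They give no percentage of events lost and no evidence on which patients would have undated records. Nor are deaths lost, since SAP 5.1.2 gives incomplete death dates their own rule and SAP 7.4.2 summarises deaths separately. The size cannot be derived from the documents and is probably small. The study is descriptive, so no test or error rate is affected.

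**What to change.** Before database lock, add to SAP 5.1.2 or 7.4.1 that an AE with a missing start date or start year is counted as treatment-emergent unless its recorded end date precedes the first roll-over dose, or other recorded data show onset before that dose or after day 84 (LAR) or day 30 (s.c.) following the last dose. End dates are not imputed, so the end-date exception applies only where the recorded part is enough to show it.

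Keep the date blank in listings and footnote in each table how many such AEs it contains. For a patient who received both formulations, count the event in the overall column and assign the formulation column by a rule stated in advance. The registry tables count occurrences by the gap between one event's end and the next event's start, so say there how an undated record is counted.

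The cost is a short passage of text and one derived flag, with no new data. AE counts become slightly less favourable, and a few pre-dose or post-window events may be counted. The footnote lets a reader judge how many.
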